Protocol Number: UCCI-HN-17-01/CA209-997

Version **Version 5, 9 October 2019**

Title: A Single Arm Phase 2 Study of Adjuvant Nivolumab after salvage resection in head and neck squamous cell carcinoma patients previously treated with definitive therapy

IND Number: 135562

Coordinating Center: University of Cincinnati

Principal Investigator: [name], PhD
[name]
[name]
[contact]
[contact]
[contact]

[name]
[name]
[name]
[contact]
[contact]

STUDY SYNOPSIS

Protocol Title: A Single Arm Phase 2 Study of Adjuvant Nivolumab after salvage resection in head and neck squamous cell carcinoma patients previously treated with definitive therapy.

Study Phase: II

Study Population: Subjects with head and neck squamous cell carcinoma (HNSCC) must have local recurrent disease after undergoing prior definitive therapy and be amenable to salvage resection.

Objectives:

Primary Objective and Hypothesis:

1. **Objective:** Evaluate the efficacy of an adjuvant treatment with Nivolumab in patients with resected HNSCC using disease-free survival (DFS) at 2-years.
 - **Hypothesis:** Using Nivolumab after salvage resection will increase DFS in patients with resected HNSCC.

Secondary Objectives and Hypotheses:

1. **Objective:** Determine the frequency of Grade 3 and 4 adverse events of Nivolumab when administered in patients after salvage resection of HNSCC.
 - **Hypothesis:** Single agent Nivolumab will be safe, and serious adverse events that occur will be managed without causing any interruption to Nivolumab administration.
2. **Objective:** Determine all grades of adverse events of Nivolumab when administered in patients after salvage resection of HNSCC.
 - **Hypothesis:** Single agent Nivolumab will be safe, and any grade adverse events that occur will be managed without causing any interruption to Nivolumab administration.
3. **Objective:** To estimate the 1-year DFS using Nivolumab in patients with resected HNSCC.
 - **Hypothesis:** Using Nivolumab after salvage resection will increase DFS in patients with resected HNSCC.

Exploratory Objectives:

1. **Objective:** Evaluate resected tumor specimens for CD4, CD8 and T reg ratios. The study will also determine PD-L1 expression on tumor and surrounding infiltrating cells along with KI-67 and granzyme expression in tumor tissue. This analysis will aim to provide a pre-PD1 inhibitor immunophenotype that can be assessed from tumor tissue to identify markers that determine relapse.
2. **Objective:** Study peripheral blood T cell response after anti-PD1 treatment by multi-

color flow cytometry to determine type of immune response on peripheral T cells.

3. **Objective:** Identify an inflammatory gene signature by RNA sequencing in tumor tissue that correlates with those who did not relapse versus those who did.

[figure not shown]
Study Design:

This study will be a 1-arm phase II trial including 39 patients with head and neck squamous cell carcinoma (HNSCC) eligible for salvage resection after definitive radiation +/- chemotherapy. Patients who undergo curative intent salvage resection will be screened and consented to receive Nivolumab following resection. Patients will receive Nivolumab every 4 weeks. Nivolumab will continue for 6 months (6 doses) as shown in schema.

For correlative studies, archived biopsy samples and/or resection tissue will be assessed by H&E and IHC for immune phenotype. Blood samples will also be collected for correlative studies.

Patients will be followed every 4 weeks during treatment, followed by a 30-day safety visit and then every 3 months thereafter for disease and survival status. Patients will be assessed for 1 and 2-year disease free survival (DFS) as well as for toxicity during treatment.

Trial Diagram:

Study Population:

For entry into the study, the following criteria MUST be met:

Key Inclusion Criteria:

- Histologically or cytologically confirmed head and neck squamous cell carcinoma (HNSCC).
- Prior definitive therapy with chemo-radiotherapy or radiation alone.
- Patients must have undergone salvage resection with curative intent.
- Adult subjects ≥ 18 years of age.
- Adequate bone marrow and organ function.
- ECOG Performance status ≤ 2 .
- Must be able to understand and sign written informed consent.

Key Exclusion Criteria:

- Patients who did not receive radiotherapy as prior definitive treatment.
- Patients who continue to have gross measurable residual disease after salvage surgery.
- Patients who underwent salvage surgery for palliative purposes i.e. for symptom control.
- Uncontrolled intercurrent illness including, but not limited to, ongoing significant or serious active cardiovascular disease, liver disease, renal disease, infection, psychiatric illness or situations that would limit the patient's ability to participate.
- Patients attempting to conceive, and pregnant or nursing women are excluded from this study.
- Autoimmune disease or other pro-inflammatory conditions other than treated stable asthma or minor allergies (such as seasonal allergies).
- A second malignancy other than HNSCC in the last 3 years. Curatively treated basal cell carcinoma or squamous cell carcinoma of the skin, or curatively treated cervical intraepithelial neoplasia (CIN) are acceptable and are not exclusionary.
- Patients with metastatic disease.
- Any patient requiring systemic corticosteroids or other immune modulatory medications.
- History of symptomatic interstitial lung disease.

Endpoints:

Primary Endpoint

1. Efficacy: measured from the time of treatment allocation to the time of discovery of the first evidence after initiation of investigational treatment of any tumor (local, regional, metastatic, or second primary) or death from any cause. DFS at 2-year will be the primary efficacy endpoint.

Secondary Endpoints

1. Safety: As determined by CTCAE v5.0 and ability to complete a minimum of six months of adjuvant Nivolumab treatment and an expected Grade 3 or 4 adverse event rate similar to Checkmate-141 trial.
2. Safety: As determined by CTCAE v5.0 and ability to complete a minimum of six months of adjuvant Nivolumab treatment and an expected all grade adverse event rate similar to Checkmate-141 trial.
3. Efficacy: DFS at 1-year will be the secondary efficacy endpoint.

Exploratory Endpoints

1. Identifying tumor immunophenotype in those who relapsed versus those who didn't and peripheral blood T cell changes before and after anti-PD1 therapy.

Study Drug:

Nivolumab will be available as an injection at 100mg/10 ml (10 mg/ml) or 40mg/4 ml (10mg/ml) and will be administered at a flat dose of 480 mg every 4 weeks.

Study Assessments:

The primary objective is to assess efficacy of Nivolumab in these patients who have been subjected to multiple modalities of treatment using DFS at 2-years. Each subject will be assessed to evaluate for potential new or worsening AEs as specified in the Trial Flow Chart and more frequently if clinically indicated. Adverse events will be graded and recorded throughout the study and during the follow-up period according to NCI CTCAE Version 5.0. Toxicities will be characterized in terms regarding seriousness, causality, toxicity grading, and action taken with regard to trial treatment.

Sample Size Justification:

We expect that the use of the Nivolumab-based adjuvant therapy will improve 2 year disease-free survival (DFS) by 20%. The optimal single-arm two-stage design with time-to-event endpoints will be used to test the null hypothesis that DFS at 2 years $\leq 33\%$, which is based on historic data, versus the alternative that DFS at 2 years $\geq 53\%$, by a one-sided, one-sample log-rank test with the power of 80% at a 5% significance level. After 17 patients are entered in the first stage, the trial will be temporarily suspended to new enrollment to allow for an interim statistical analysis. The trial will be terminated if the test statistic at stage 1 > 0.76 .

If the trial goes on to the second stage, a total of 35 patients will be studied. We reject the null hypothesis if the test statistic at stage 2 > -1.62 . Considering a drop-out rate of 10%, a total of 39 patients are expected to be required for this study.

Efficacy Analyses:

All patients who received ≥ 1 dose of Nivolumab will be assessed for efficacy and the primary and secondary endpoints for efficacy will be disease-free survival (DFS) at 2- and 1-year, respectively. DFS is defined as the duration from the time of treatment allocation to the time of discovery of the first evidence after initiation of investigational treatment of any tumor (local, regional, metastatic, or second primary) or death from any cause. The distribution of DFS will be summarized by Kaplan-Meier curve, and the median DFS and its associated 95% confidence interval (CI) will be calculated. The DFS at 1- and 2-years will also be summarized with its associated 95% CIs. In addition, patients will be censored at the end of the study (end of two years of follow-up of last patient enrolled), and both disease free survival (or DFS defined as no recurrence by the time of censoring) and overall survival (OS, defined as being alive by the time of censoring) will be assessed using Kaplan-Meier curves.

Safety Analyses:

The All-Patients-as-Treated (APaT) population will be employed for safety analyses. The secondary safety endpoints are the Grade 3 and 4 adverse events and the all adverse event graded from 1 to 5. Both safety secondary endpoints are dichotomous and will be summarized using frequency (in %). In addition, the 95% CI's will be calculated using the exact method, i.e. the binomial distribution method. We expect to reach 13% of Grade 3 and 4 adverse events and 58.9% of all Graded Adverse events, similar to those reported in the Checkmate 141 study.

Biomarker Assessments:

All biomarker measures will be summarized with descriptive statistics, i.e., percentages for categorical outcomes and means/medians for continuous outcomes, with corresponding standard errors and 95% confidence intervals. Responses will be tabulated by determined response and toxicities will be tabulated by type and grade. For IHC, the percentage of positive cells per area will be multiplied by the staining intensity for each tumor to determine quantitative expression pre- and post-treatment; a 25% change in expression will be considered a positive response. Patient level exploratory endpoints will be summarized using frequency (in %) if they are dichotomous or categorical and mean (std) if they are numerical respectively. Endpoints will be assessed of relations or associations using regression models, ANOVA models and logistical models respectively to accommodate numerical and categorical types of dependent and independent variables (i.e. endpoints).

Accrual Rate:

At the University of Cincinnati, we see approximately 300-350 new cases of HNSCC per year. Of those, approximately 100-150 stage III/IV HNSCC are treated with radiation +/- chemotherapy. Our institution conducted a retrospective analysis and identified twenty-eight patients over a 1-year period that were initially treated with definitive concurrent CRT or RT alone who subsequently developed local recurrence and required salvage resection. Based on this, we expect to accrue approximately 1-2 patients per month at UC. From the similar consideration to UC, we expect that the accrual rates would be 2 patients per month at Karmanos Cancer Institute. That will yield a combined 2-institution effective accrual rate of 3-4 patients per month. Thus we expect enrollment for this phase II study to be completed within 10-13 months based on 39 patients.

TABLE OF CONTENTS

STUDY SYNOPSIS	1
SECONDARY OBJECTIVES AND HYPOTHESES:	1
EXPLORATORY OBJECTIVES:	1
1.0 BACKGROUND & RATIONALE.....	1
1.1 PRODUCT DEVELOPMENT BACKGROUND	1
1.1.1 MECHANISM OF ACTION AND RATIONALE FOR USE OF DRUG	1
1.2 ADJUVANT TREATMENT IN HEAD AND NECK CANCER.....	2
2.0 RATIONALE.....	3
2.1 RATIONALE FOR THE TRIAL AND SELECTED SUBJECT POPULATION	3
2.2 EFFICACY ENDPOINTS.....	3
2.3 SAFETY ENDPOINTS	3
2.4 BIOMARKER RESEARCH/ENDPOINTS RATIONALE	4
3.0 ETHICAL CONSIDERATIONS	4
3.1 GOOD CLINICAL PRACTICE	4
3.2 INSTITUTIONAL REVIEW BOARD.....	4
3.3 INFORMED CONSENT	4
4.0 METHODOLOGY/INVESTIGATIONAL PLAN	5

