- g) On Day 1 and week 5, ensure correlative samples are collected prior to protocol treatment. A 3rd sample should be collected at the end of treatment visit. Correlatives will be placed in four 10ml lavender EDTA tubes.
- h) Thyroid function labs can be checked at physician's discretion on post treatment follow up.
- i) SAEs should be evaluated out to 100 days after drug discontinuation. All AEs should be followed until \leq Grade 1 or new therapy has begun. All non-serious AEs must be followed continuously for at least 30 days.
- j) Adjuvant treatment must be started 28-77 days after salvage surgery.
- k) May be assessed by phone or clinic visit
- l) Post discontinuation visit should occur at 30 days +/-3 days as above, or before new therapy begins, whichever occurs first.
- m) Medical History from last 10 years should be included
- n) Height also required only at screening
- o) Labs must be collected within 10 days of first treatment and within 72 hours prior to subsequent treatments. Screening labs can be used for Day 1 as long as within window.
- p) Must be collected within 72 hours of Day 1.
- q) Subjects who discontinue for reasons other than progressive disease will have post-treatment follow-up for disease status until disease progression, initiating a non-study cancer treatment, withdrawing consent or becoming lost to follow-up or the end of the study whichever occurs first. After documented disease progression each subject will be followed by telephone for overall survival until death, withdrawal of consent, or the end of the study, whichever occurs first.
- r) Protocol treatment must begin only after eligibility criteria are confirmed by the UC PI (registration)

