7.4.4 ASSIGNMENT OF SCREENING/STUDY NUMBER

All consented subjects will be given a unique screening number that will be used to identify the subject for all procedures that occur prior to eligibility being confirmed. Protocol treatment must begin only after eligibility criteria are confirmed by the UC PI. Sites must provide notification of consent and evidence of eligibility to the UC PI. Each subject will be assigned only one screening

number. Screening numbers must not be re-used for different subjects. The University of Cincinnati will provide any sub-sites with instructions for the methods to be used in assigning screening information to potential subjects.

Any subject who is screened multiple times will retain the original screening number assigned at the initial screening visit. The screening number will be their study number as well once they are allocated to treatment.

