7.7.1 SCREENING

Potential subjects will be evaluated to determine that they fulfill the entry requirements as set forth in eligibility requirements. Visit requirements are outlined in Section 6.0 – Trial Flow Chart.

Results of a test performed prior to the subject signing consent as part of routine clinical management are acceptable in lieu of a screening test if performed within the specified time frame. Screening procedures are to be completed within 28 days prior to the first dose trial treatment except for the following:

- Laboratory tests and ECOG PS are to be performed within 10 days prior to the first dose of trial treatment.
- For women of reproductive potential, a serum pregnancy test will be performed within 72 hours prior to the first dose of trial treatment. A urine test may be considered if serum test is not appropriate.
- Any tumor imaging done pre-operatively, does not need to meet the 28 day pre-dose requirement for screening procedures

Subjects may be rescreened after initially failing to meet the inclusion/exclusion criteria and they have not yet started treatment, however, re-screening tests will not be covered by study. Results from assessments performed during the initial screening period are acceptable in lieu of a repeat screening test if performed within the specified time frame and the inclusion/exclusion criteria is met. Protocol treatment must begin only after eligibility criteria are confirmed by the UC PI.

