9.0 STATISTICAL ANALYSIS PLAN

9.1 EFFICACY ANALYSIS

All patients who received ≥ 1 dose of Nivolumab will be assessed of efficacy and the primary and secondary endpoints of efficacy will be disease-free survival (DFS) at 2- and 1-year, respectively. DFS is defined as the duration from the time of treatment allocation to the time of discovery of the first evidence after treatment of any tumor (local, regional, metastatic, or second primary) or death from any cause. The distribution of DFS will be summarized by Kaplan-Meier curve, and the median DFS and its associated 95% confidence interval (CI) will be calculated. The DFS at 1- and 2-years will be also summarized with its associated 95% CIs. In addition, patients will be censored at the end of the study, and both disease free survival (or DFS defined as no recurrence by the time of censoring) and overall survival (OS, defined as being alive by the time of censoring) will be assessed using Kaplan-Meier curves.

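### DFS is timed from an undated treatment allocation, but events and the efficacy set begin at the first dose, so any gap between the two is event-free by construction

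*Combined protocol and SAP*

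**What the plan says.** Three rules bear on the primary endpoint.

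- **Start of the clock.** The synopsis (Primary Endpoint) has DFS "measured from the time of treatment allocation to the time of discovery of the first evidence after initiation of investigational treatment of any tumor", with death from any cause also an event. Allocation is likewise the origin in the synopsis Efficacy Analyses and in Sections 2.2, 9.1 and 9.5.1.
- **Event rule.** Both synopsis statements count tumour evidence found after study treatment has started. Sections 2.2, 9.1 and 9.5.1 are looser; Section 9.1, for example, has "the time of discovery of the first evidence after treatment of any tumor".
- **Analysis set.** The synopsis states: "All patients who received ≥ 1 dose of Nivolumab will be assessed for efficacy". Section 9.1 gives the same set.

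Allocation has no definition and no date. Section 7.4.4 mentions it only in passing: "The screening number will be their study number as well once they are allocated to treatment". Sections 5.6, 6.0 (note r), 7.4.4 and 7.7.1 require eligibility to be confirmed before treatment begins, and 5.6 and 6.0 label that step registration. On timing, Section 7.7.1 says "Screening procedures are to be completed within 28 days prior to the first dose trial treatment", with laboratory tests and ECOG status required within 10 days of the first dose.

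**The concern.** The clock can start before the point at which an event can count. If a patient is allocated some days before the first dose, a tumour found in those days is not an event under the synopsis wording. A patient who dies in those days is never dosed and so never enters the efficacy set. The days are therefore event-free by definition, but they still count as DFS time and as exposure that generates expected events in the log-rank statistic.

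In a randomised trial both arms would share this. Here the comparator is a fixed 33% at 2 years, so nothing offsets it. At stake are a slight upward shift in 2-year DFS, a higher false-positive rate and a lower chance of stopping at stage 1 when the drug does nothing.

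Separately, the looser event wording in Sections 2.2, 9.1 and 9.5.1 could be read as after treatment has ended, which is not what the synopsis says.

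**Working it through.** **Inputs from the documents.** Null 2-year DFS 33%, alternative 53%; one-sided 5%, power 80%; stage 1 after 17 patients, stop if the statistic exceeds 0.76; 35 patients in total; final boundary -1.62; 10% drop-out (synopsis, Sample Size Justification). Accrual 3-4 per month (Section 9.4). Relapse follow-up 2 years (Section 7.5.8).

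**Assumptions.** Exponential DFS. Gap lengths are not given; 10 days is taken from the laboratory/ECOG rule and 28 days from the screening window. The statistic is W = (O - E)/sqrt(E), with O observed and E expected events, and the null is rejected when W is below -1.62, the direction in which fewer events favour the drug. The direction of the printed final rule, and Section 9.3's figure of 39 for stage 2, are separate matters.

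**The plan's own figures.** 35/0.9 = 38.9, so 39 enrolled, as stated. With 24 months of follow-up per patient, the large-sample two-stage calculation gives type I error 0.048-0.050 and power 0.78-0.80 at 2-4 patients per month. That agrees with the stated design to rounding.

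**Shift in 24-month DFS with no drug effect.**
Null hazard: -ln(0.33)/24 = 0.0462 per month. With a gap of g months, 24-month DFS is exp(-0.0462 × (24 - g)) = 0.33 × exp(0.0462 × g), at 30.44 days per month.

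- 7 days: g = 0.230, 0.33 × 1.0107 = 0.3335
- 10 days: g = 0.329, 0.33 × 1.0153 = 0.3350
- 28 days: g = 0.920, 0.33 × 1.0434 = 0.3443

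The shifts are about 0.35, 0.5 and 1.4 points, against a target difference of 53 - 33 = 20 points.

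**Effect on the decision rule.** Simulation with n = 35, 3.5 patients per month, no drop-out, interim at the 17th entry and 24 months of follow-up from allocation. A fixed event-free gap precedes each patient's exponential time, while expected events accrue from allocation.

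| Gap | Type I error | Stage 1 stop, ineffective drug |
|---|---|---|
| 0 days | 0.039 | 22% |
| 7 days | 0.045 | 17-18% |
| 10 days | 0.049 | 16% |
| 14 days | 0.054 | 14% |
| 28 days | 0.07 | 8% |

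If gaps are spread evenly over 0-10 days, type I error is about 0.044; over 0-28 days it is about 0.053-0.055. The stage 1 column depends on when the interim is taken. It moves most because early follow-up is short, so a few guaranteed days are a larger share of it.

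**The case against.** The gap itself is not documented. Nothing in the plan equates allocation with registration, and in a single-arm trial allocation could be the day of the first dose, in which case there is no bias. A reader might infer that every patient receives guaranteed time; the text supports that only for patients whose allocation precedes the first dose. This objection stands.

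A reader might also take 28 days as typical. It is the outer limit for screening procedures. Eligibility depends on laboratory values and ECOG status that must fall within 10 days of the first dose, so confirmation should normally come inside that window. This stands too: at 10 days the shift is 0.5 points, against a binomial standard error of about 8 points (sqrt(0.33 × 0.67/35) = 0.079), and simulated type I error does not go materially above 5%.

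Follow-up for relapse is every 12 weeks ± 4 weeks, imaging is required only on suspicion, and no disease imaging is scheduled between registration and first dose. Few relapses would be found in the gap, and its length lies within the detection interval. That confirms the effect is small, but coarse detection does not cancel a shift in one direction.

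Finally, a reader might infer that the trial's comparison with history always favours the drug. The documents do not support that, because the time origin of the historic 33% is not given. If it ran from surgery, the 28-77 days between surgery and first dose would matter more than this gap.

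**Conclusion.** The start of the clock, the event rule and the analysis set do not agree, and the origin of the primary endpoint is undefined. Where allocation precedes the first dose, the gap lengthens DFS against the fixed null: by about 0.35-0.5 points at 24 months for 7-10 days, and by 1.4 points at the 28-day outer bound. Type I error stays at or below about 5% up to 10 days and reaches about 7% at 28 days. These figures rest on exponential DFS, an assumed common gap and rejection for fewer events. They do not show that the planned error rate is breached in practice, or that the net comparison with the historic rate is biased in a known direction. This is a minor point, worth making because correcting it is free.

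**What to change.** Make the same two edits in all five statements of the definition (synopsis Primary Endpoint, synopsis Efficacy Analyses, Sections 2.2, 9.1 and 9.5.1):

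1. Replace treatment allocation with the date of first nivolumab dose as the origin of DFS, including the 1- and 2-year values.
2. Use the synopsis event wording throughout, so that Sections 2.2, 9.1 and 9.5.1 refer to evidence found after the start of study treatment.

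The date of first dose is recorded in any case, so no data, visits or patients are added and the sample size is unchanged. The time origin of the historic 33% should be stated separately; these edits do not resolve it.

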7.5.8 ASSESSMENT OF DISEASE

Patients will be assessed for recurrence every 3 months after completion of treatment as above. For patients felt to have a relapse at any time, a thorough ENT exam as well as a repeat biopsy is recommended to confirm relapsed disease. Follow-up imaging in 4-8 weeks is also acceptable if biopsy is not yet felt to be necessary or is non-diagnostic. Patients will be followed clinically every three months and any concern for relapsed disease or progression should trigger either imaging or biopsy for confirmation. Patients will be followed for relapse for a total of 2 years.

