7.7.4 FOLLOW-UP VISITS

Patients will move into follow-up after completion of last dose of Nivolumab. They will continue follow-up every 12 weeks +/- 4 weeks either by a doctor visit or by phone (if being seen by outside oncologist) for up to 2 years to monitor for relapse, or until time of withdrawal of consent, or death, whichever comes first. If patients develop a relapse, they will be followed for survival. Every effort should be made to confirm relapse if suspected.

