9.3 SAMPLE SIZE

We expect that the use of the Nivolumab-based adjuvant therapy will improve 2 year disease-free survival (DFS) by 20%. The optimal single-arm two-stage design with time-to-event endpoints(Kwak & Jung, 2014) will be used to test the null hypothesis that DFS at 2 years $\leq 33\%$, which is based on the historic data, versus the alternative that DFS at 2 years $\geq 53\%$, by a one-sided, one-sample log-rank test with the power of 80% at a 5% significance level. After 17 patients are entered in the first stage, the trial will be terminated if the test statistic at stage 1 > 0.76 . If the trial goes on to the second stage, a total of 39 patients will be studied. We reject the null hypothesis if the test statistic at stage 2 > -1.62 . Considering a drop-out rate of 10%, a total of 39 patients are needed for this study.

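### Relapse-monitoring windows conflict with end-of-study DFS censoring, and the primary log-rank test has no censoring rule of its own

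*Combined protocol and SAP*

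**What the plan says.** Four places describe how long disease status is followed, and they do not agree.

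- Section 7.5.8: "Patients will be followed for relapse for a total of 2 years".
- Section 7.7.4: patients enter follow-up after their last dose and are then contacted "for up to 2 years to monitor for relapse, or until time of withdrawal of consent, or death, whichever comes first".
- Section 4.5 and note q to the flow chart in Section 6.0: disease status is followed until progression, non-study treatment, withdrawal, loss to follow-up or the end of the study. The opening words refer to subjects who discontinue for reasons other than progression.
- Synopsis, Study Design: three-monthly follow-up for disease and survival status, with no upper limit.

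On censoring, the Efficacy Analyses paragraph of the Synopsis says "patients will be censored at the end of the study (end of two years of follow-up of last patient enrolled"), and Section 9.1 repeats "patients will be censored at the end of the study" without defining that date. In both places the sentence is introduced as an addition and concerns Kaplan-Meier curves for DFS and OS. The primary test is specified in Section 9.3 as a "one-sided, one-sample log-rank test with the power of 80% at a 5% significance level". Neither Section 9.3 nor Section 9.6.1 says when event-free patients are censored for that test.

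**The concern.** The one-sample log-rank statistic compares observed events with the events expected under the null, and the expected count grows with every unit of follow-up credited to each patient. The censoring time is therefore a direct input to the primary test. If a site stops looking for relapse at 24 months under Section 7.5.8 while the analysis credits the patient as disease-free to study end, the expected count rises over a period in which relapse cannot be observed. The error always favours the drug.

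If instead time is cut at 24 months to match the monitoring, the bias disappears. But the design then has less information than the follow-up to study end under which the stated 80% can be reproduced.

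**Working it through.** **Inputs.** From Section 9.3: null and alternative 2-year DFS of 33% and 53%, one-sided 5%, 17 patients at stage 1, bounds 0.76 and -1.62. From the Synopsis: 35 patients in total (Section 9.3 prints 39 at the same place). From Section 9.4: accrual of 3–4 per month, complete in 10–13 months.

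**Assumptions not in the documents.** Exponential DFS, uniform accrual, no random loss among the 35, and an interim look when patient 17 enters. Rejection is taken as Z ≤ -1.62, because benefit makes Z = (O - E)/√E negative, although the plan prints the inequality the other way.

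**Horizons.**
- Study end for the first patient: 2 + 10/12 = 2.83 to 2 + 13/12 = 3.08 years, longer if the stage 1 enrolment pause lasts.
- Section 7.7.4 window: the sixth dose is at week 21, 20 weeks after the first, so 2 + 20/52 ≈ 2.4 years from first dose.

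**Hazards.** Null: -ln(0.33)/2 = 0.5543 per year. Alternative: -ln(0.53)/2 = 0.3174 per year. Ratio 0.573.

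**Reproducing the stated power (single-stage normal formula, n = 35, follow-up to study end, 3 per month).** Under the alternative, O = 19.04 and E = 33.25, so the mean of Z is (19.04 - 33.25)/√33.25 = -2.464, with SD 0.956. Power = Φ((-1.645 + 2.464)/0.956) = 80.4%. At 4 per month it is 79.5%. The stated 80% is reproduced.

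**Same formula, everyone capped at 24 months.** O = 35 × 0.47 = 16.45. E = 16.45 × 0.5543/0.3174 = 28.73. Mean Z = (16.45 - 28.73)/√28.73 = -2.290, SD 0.920. Power = Φ((-1.645 + 2.290)/0.920) = 75.8%.

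**Two-stage design with the printed bounds.** Power is about 77–80% with follow-up to study end and about 74–76% with the cap. An example by analytic calculation with the exact variance, at 42 per year, is 77.7% falling to 74.0%.

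**Bias under the null (relapse sought for 24 months, time credited to study end).** Observed events are 35 × 0.67 = 23.45. The 33% still event-free at 24 months are each credited, on average, with half the accrual period more.
- 3 per month: accrual lasts 35/36 = 0.972 year, so extra E = 35 × 0.33 × 0.5543 × 0.486 = 3.11 and E = 26.56. Z shifts by -3.11/√26.56 = -0.60.
- 4 per month: accrual lasts 35/48 = 0.729 year, so extra E = 35 × 0.33 × 0.5543 × 0.365 = 2.33 and E = 25.78. Z shifts by -2.33/√25.78 = -0.46.

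**Simulated one-sided type I error of the two-stage rule, n = 35, 3–4 per month.**

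| Handling after the relapse window | Type I error |
|---|---|
| Relapse sought to study end | about 4% |
| Capped and censored at 24 months | about 4% |
| 24-month window, time credited to study end, all later events unseen | about 10–14% |
| Same, half of later events unseen | 7–8% |
| Same, 30% of events are deaths still seen | about 8–10% |
| Section 7.7.4 window, time credited to study end | about 5–6% |

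**Kaplan-Meier.** The handling of time after 24 months cannot change the 1- or 2-year estimates. The later part of the curve can change, and so can the median if it falls there. Under the alternative the median would be ln 2/0.3174 = 2.18 years.

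**The case against.** A reader might infer that relapse monitoring simply stops at 2 years for every patient. The documents do not establish that. Section 4.5 and note q carry disease-status follow-up to the end of the study, and note q is attached to the post-treatment column of the flow chart. Their opening words could limit them to early discontinuers, but that is not the only reading. On the broader reading no bias arises. This stands: the finding is a contradiction to reconcile. It does not remove the concern, because a site following Section 7.5.8 and a site following Section 4.5 would collect different data.

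A second objection is that the end-of-study sentence belongs to the Kaplan-Meier curves, so applying it to the log-rank test reads in something the plan does not say. This also stands in part. But it is the only DFS censoring rule in the plan. Either it governs the primary test or that test has none, and both cases need a sentence.

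A reader might also conclude that the cap takes power from 80% to 74%. That sets a single-stage figure against a two-stage one. The two-stage calculation that gives 74% with the cap gives only about 77–78% without it. If all 39 enrolled patients are evaluable, the capped two-stage power is about 76–79%.

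Finally, 10–14% is a worst case: it needs the 7.5.8 window, time credited to study end and every later event missed, deaths included. With a front-loaded hazard (Weibull shape 0.5 to 0.7, an assumption, still 33% at 2 years) simulation gives 7–10%.

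**Conclusion.** The point holds as a conflict between the stated monitoring windows and the only stated censoring date, together with a missing censoring rule for the primary test. Combining Section 7.5.8 with end-of-study censoring as written would bias the test towards the drug. The false-positive rate could then be more than double the nominal 5%, and it would be close to nominal under the 7.7.4 window. The result depends on which passage is followed, so the choice should be made before the analysis. Capping cleanly at 24 months avoids the bias at a cost of about 3–5 points of power: roughly 77–80% to 74–76% two-stage, or 80% to 76% single-stage. These sizes rest on the assumptions listed with the inputs, chiefly exponential DFS and uniform accrual. The documents do not support saying that monitoring definitely ends at 24 months, or that true power is 74% where 80% was claimed.

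**What to change.** 1. State one relapse-monitoring window, with its starting point, and use it in Sections 4.5, 7.5.8, 7.7.4 and 9.1 and in flow-chart note q. Define the end of study in Section 9.1 as the Synopsis does.
2. Add to Section 9.1 that, for the one-sample log-rank test and for the DFS curves, patients without an event are censored at their last disease assessment and not at study end. This removes the bias whichever window is chosen.
3. If the window is capped at 24 months, restate the power for 35 patients under that rule, naming the calculation used (two-stage or single-stage).

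The cost is a few sentences. A window running to study end adds up to about 12 months of 12-weekly contacts for early enrollees, which Section 7.7.4 already allows by phone for patients seen by an outside oncologist. A 24-month cap costs nothing operationally but lowers the stated power slightly.
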